9.1 Individual Results

No laboratory data will be collected. Individual results will not be provided to participants enrolled in this study. Data collected will be used for study purposes including any data already collected. Should someone decide to withdraw consent no new data will be collected, but data on hand will continue to be used.

A description of this clinical trial will be available on <http://www.clinicaltrials.gov> as required by US Law.

9.2 Aggregate Results

Data will be stored on a university computer that is password protected and that has encryption capabilities for a period of 6 years post the end of the study per university policy. Patients can contact the primary investigator to inquire about their data at any time during the study.

Reducing Nausea and Vomiting During Cesarean Section with Regional Anesthesia: Is the Application of Scopolamine Patch with or without Intra-operative Acupressure Point P6 Stimulation more effective than Intra-operative Acupressure Point P6 Stimulation alone?

By [name]

Did patient have more than 700cc blood loss? (Y/N) _____ cc

Efficacy of sensory block for C/S _____ (1-4)
(1 = no complaints 2 = + complaints 3 = + sedation N2O or IV 4 = G/A)

Nausea and vomiting treatment satisfaction _____ (0-10, 0 = not satisfied, 10 = extremely satisfied)
Overall satisfaction _____ (0-10, 0 = not satisfied, 10 = extremely satisfied)

Reducing Nausea and Vomiting During Cesarean Section with Regional Anesthesia: Is the Application of Scopolamine Patch with or without Intra-operative Acupressure Point P6 Stimulation more effective than Intra-operative Acupressure Point P6 Stimulation alone?

By [name]

APPENDIX II:

Nausea Score

**Comments:**

The methods below are consistent with those mentioned in the protocol, after eliminating mention of unneeded procedures for looking at effectiveness of treatment. The methods also clarify the adjustment for multiple testing on the two primary outcomes.

## **Methods**

Means (standard deviations) were used to describe the distributions of continuous variables while frequencies (percentages) were used for categorical variables. Using intent-to-treat analyses, Analysis of Variance (ANOVA) was used to summarize the effect of treatment on satisfaction scores as well as ratings of nausea at time points 1 through 4 while chi-square was used for occurrence (yes/no) of nausea and vomiting overall all time points and vomiting at time points 1 through 4.

A Bonferroni corrected p-value was calculated for the treatment effect on the two main outcomes, presence of vomiting and presence of nausea, such that an adjusted p-value from each test equaled the nominal p-value multiplied by 2.

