Robert Wood Johnson
Medical School

Department of Anesthesiology and
Perioperative Medicine
Rutgers, The State University of New Jersey
[name]
[name]

<http://rwjanesthesiology.rwjms.rutgers.edu>
p. [contact]
f. [contact]

August 3, 2022

Official Title:

Reducing Nausea and Vomiting During Cesarean Section with Regional Anesthesia: Is the Application of Scopolamine Patch with or without Intra-operative Acupressure Point P6 Stimulation more effective than Intra-operative Acupressure Point P6 Stimulation alone?

Document:

Study Protocol

NCT02960113

Title of Project:

**Reducing Nausea and Vomiting During Cesarean Section
with Regional Anesthesia: Is the Application of
Scopolamine Patch with or without Intra-operative
Acupressure Point P6 Stimulation more effective than
Intra-operative Acupressure Point P6 Stimulation alone?**

Principal Investigator:

[name]

Funding Source(s):

Rutgers Robert Wood Johnson Medical School

1. Purpose/Specific Aims

1. The purpose of this study is to compare the effectiveness of reducing intra-cesarean section nausea and vomiting with regional anesthesia in subjects who will receive scopolamine patch with acupressure point P6 stimulation versus subjects that receive just scopolamine patch versus subjects that receive just acupressure point P6 stimulation.

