1.2 Hypothesis

We suspect that there will be a difference in outcomes when comparing the three methods research arms and that one or more research arms will have a significantly lower mean rate of nausea and vomiting during cesarean delivery.

2. Background and Significance

Cesarean section is a procedure utilized by obstetricians in which an infant is delivered through a surgical incision in the mother's abdomen and uterus. This procedure requires adequate anesthesia usually obtained through one of three modalities: general, spinal, and/or epidural anesthesia. With general anesthesia, the patient is completely unconscious with the utilized agents affecting the entire body. Anesthesia-related maternal complications and mortality are lower when general anesthesia is avoided[1]. Regional anesthesia is the preferred option of healthcare providers when comparing the risks and benefits to the mother and her fetus[2].

Regional anesthesia, including spinal and epidural anesthesia, usually involves injecting varying concentrations and combinations of bupivacaine, ropivacaine, and fentanyl into the

Reducing Nausea and Vomiting During Cesarean Section with Regional Anesthesia: Is the Application of Scopolamine Patch with or without Intra-operative Acupressure Point P6 Stimulation more effective than Intra-operative Acupressure Point P6 Stimulation alone?

By **[name]**

subarachnoid or epidural spaces respectively [3, 4]. With epidural anesthesia, the mother is awake for the procedure and does not feel pain in the anesthetized area. Utilized anesthetic agents are continuously injected into the epidural space around the spinal cord that is usually occupied by fat. With spinal anesthesia, the mother is also awake but utilized agents are directly injected into the cerebral spinal fluid in lower doses than would be normally utilized with epidural anesthesia[5]. The advantages of these methods are effective pain relief without appreciable motor blockade, reduced risk of complications normally seen with general anesthesia, increased infantile APGAR scores at one and five minutes, and earlier bonding of mother with infant. Disadvantages include the inability to perform in mothers with coagulopathies or skin infections overlying the spine, increased reports of pain, and increased nausea and vomiting[4].

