3.3 Sample Size Justification

This is a randomized unblinded prospective study comparing three different research arms in parallel. There will be three groups each having 80 subjects enrolled for the study. Sample size was determined using online software (Sealed Envelope, binary outcome superiority trial) to obtain power of 90%, two-tailed test at 5% significance level to detect 90% success rate in the combination arm (Scopolamine + acupressure) compared to either of other two arms (70% success rate).

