5.3 Subject Costs and Compensation

The subject will not incur additional costs outside of standard of care costs for medication that may be performed for routine standard of care. There will be no compensation for participation in this study.

6. Data Handling

All data will be stored in a locked file in the office of the principal investigator with limited access. The link to the protected health information will be stored separately from the study files and will be destroyed after all the data has been collected and analyzed. Up to 400 subjects may sign the informed consent for participating in this trial. This number is to ensure that 80 subjects complete each study group below. Therefore, we will be replacing subjects that do not complete the study as designed.

7. Statistical Analysis

There will be 3 treatment groups each having 80 subjects enrolled for the study. The intergroup analysis for numerical variables will be performed by ANOVA. All categorical variables will be analyzed with Chi-square/Fisher test. Descriptive statistics will provide the quantitative summaries for numerical data in each group.

The difference in end surgical nausea and vomiting will be analyzed using the Mann-Whitney rank sum test. Power analysis determined that 80 patients will be necessary in each group to detect the difference in treatment in nausea and vomiting, assuming a two sided alpha of 0.05 and power of 90%.

8. Data and Safety Monitoring

There is no data and safety monitoring committee for this study. Patients will be followed for adverse effects during their participation in this study. We will use Form FDA 3500A mandatory and Form FDA 3500 voluntary reporting forms found on the FDA website, www.fda.gov.

Reducing Nausea and Vomiting During Cesarean Section with Regional Anesthesia: Is the Application of Scopolamine Patch with or without Intra-operative Acupressure Point P6 Stimulation more effective than Intra-operative Acupressure Point P6 Stimulation alone?

By [name]

9. Reporting Results

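### For the two main outcomes the plan names no between-arm contrast, estimate or interval, so it gives no inference on the title's comparisons or on the contrast used for the sample size

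*SAP*

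**What the plan says.** **The question.** The title asks: "Is the Application of Scopolamine Patch with or without Intra-operative Acupressure Point P6 Stimulation more effective than Intra-operative Acupressure Point P6 Stimulation alone"? That is two comparisons against P6 alone. Protocol section 1.2 expects "a difference in outcomes when comparing the three methods research arms and that one or more research arms will have a significantly lower" rate of nausea and vomiting. Section 3.3 sets 80 per arm to "detect 90% success rate in the combination arm (Scopolamine + acupressure) compared to either of other two arms (70% success rate"), with 90% power and a two-sided 5% test.

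**The analysis.** The SAP Methods state that "chi-square was used for occurrence (yes/no) of nausea and vomiting overall all time points and vomiting at time points 1 through 4". They add: "A Bonferroni corrected p-value was calculated for the treatment effect on the two main outcomes, presence of vomiting and presence of nausea", by doubling the nominal p-value. The SAP Comments explain the purpose: "The methods also clarify the adjustment for multiple testing on the two primary outcomes". Categorical variables are otherwise summarised by counts and percentages.

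Protocol section 7 says "All categorical variables will be analyzed with Chi-square/Fisher test" and "The difference in end surgical nausea and vomiting will be analyzed using the Mann-Whitney rank sum test". The Mann-Whitney sentence names no arms, and the test does not appear in the SAP, whose Comments say that procedures not needed for effectiveness were left out.

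**The concern.** One p-value per outcome and a factor of 2 imply, without saying so, a single three-group chi-square for each outcome. That test is valid for the first half of section 1.2, a difference somewhere among the arms. It gives no inference on the second half (which arm or arms are lower), on either comparison in the title, or on the contrast in section 3.3.

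A significant result therefore supports only the statement that the three arms are not all alike. Set beside the arm percentages, it can be taken as evidence for the combination over P6 when the data do not supply it. If pairwise chi-square tests were meant instead, the factor of 2 counts outcomes and not arm pairs, so pairwise claims have no stated error control.

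**Working it through.** **Inputs.** 80 per arm; success 90% (combination) against 70% (each single arm); two-sided 0.05; 90% power (section 3.3). The SAP's doubling makes the nominal level 0.025 per outcome. Section 3.3 does not say which outcome its success rates describe. I assume they apply to each of the two main outcomes, with success meaning absence of the event. Rates are given in the order patch / P6 / combination.

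**1. The plan's own figure.** For two arms with unpooled variance, n = (1.960 + 1.282)² × (0.9×0.1 + 0.7×0.3) / 0.2² = 10.507 × 0.30 / 0.04 = 78.8, so 79 per arm. The pooled form gives 82. The stated 80 is thus reproduced as a comparison of two arms, which the planned test does not isolate.

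**2. The three-group p-value does not depend on which arm is better.** Success counts of 56/56/72 and 72/56/56 out of 80 both give chi-square 11.93, p = 0.0026 (doubled, 0.005). Combination minus P6 is +20 points (95% CI 8 to 32) in the first case and 0 points (−14 to 14) in the second.

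**3. A case where the percentages mislead.** Hypothetical counts 56/65/72 of 80, that is 70%, 81% and 90%:
- Three-group: pooled rate 193/240 = 0.804; chi-square = (8.33² + 0.67² + 7.67²) / (80 × 0.804 × 0.196) = 10.21; p = 0.0061, doubled 0.012.
- Combination vs P6: chi-square 2.49, p = 0.115. Difference 8.75 points; SE = √(0.8125×0.1875/80 + 0.9×0.1/80) = 0.0550; 97.5% CI 8.75 ± 2.241 × 5.50 = −3.6 to 21.1 points.
- Combination vs patch: chi-square 10.0, p = 0.0016. Patch vs P6: p = 0.097.

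The planned output is a significant result with the combination on top. It would not show that the combination is not separated from P6.

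**4. How often this happens.** 1,000,000 simulated trials per scenario, Pearson chi-square without continuity correction, level 0.025.

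| Rates | Three-group test significant | Among significant trials |
|---|---|---|
| 70/70/90 | 86.8% | Combination not better than both single arms: 0.131/0.868 = 15.1%. Not better than P6: (0.868 − 0.802)/0.868 = 7.6% |
| 70/90/90 | 90% | Combination observed highest in 45%, although it equals P6 |

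**5. If pairwise tests were meant.** With three ungated pairs at 0.025 and equal arms, at least one false claim for a given outcome occurs in 5.7%, 6.4%, 6.4% and 5.6% of trials at common rates of 50%, 70%, 80% and 90%. Over two outcomes the chance is about 6% if the outcomes coincide. If they are independent it is 1 − (1 − 0.0563)² = 10.9% to 1 − (1 − 0.0641)² = 12.4%. The intended level is 5%.

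**6. If the three-group test gates the pairs.** With equal arms the false-claim rate per outcome falls to 2.2% to 2.5%. With one true null it is 2.5% (patch vs P6 at 70/70/90) and 2.1% (combination vs P6 at 70/90/90). With three arms, any two pairwise nulls together amount to the overall null, so no further split of alpha is needed.

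**The case against.** Protocol sections 1 and 1.1 pose a symmetric three-way comparison, and the three-group test fits that and the first half of section 1.2; only the title makes P6 the reference. This narrows the point. It does not remove it, because the second half of section 1.2 and section 3.3 also need specific pairs.

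Under the protocol's own 70/70/90 assumption the test is seldom misleading. The 15% requires success against both single arms, whereas the word used in section 3.3 need not mean both jointly; for P6 the figure is 7.6%. That is right, and both figures should be read together. The 45% follows largely from two arms being equal by construction, and the 56/65/72 example is chosen. They illustrate what the plan cannot distinguish; they are not error rates of the planned test.

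The pairwise reading is the less likely one, and its 12% needs independent nausea and vomiting, which the documents do not support. It matters only because the SAP leaves the reading open.

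Finally, counts reported by arm let a reader compute each difference and interval. That is so, but it leaves the choice of comparison until after the results are seen, in an unblinded trial. The SAP's past tense may also mean that the analysis has been run, in which case the gain lies in reporting.

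**Conclusion.** The concern holds. Nothing in either document names an arm pair, an estimate or an interval for the two main outcomes. The three-group test is valid, but followed as written the plan cannot answer the title question or test the contrast that gave 80 per arm. The size depends on the true rates. At the design rates, 15% of significant trials lack support for the combination over both single arms, and 7.6% lack it for the combination over P6. These figures assume that section 3.3's rates hold for each outcome, with 80 analysed per arm. The absence of named contrasts does not depend on those assumptions. This should be fixed, and the fix is cheap.

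**What to change.** State that each main outcome is tested by a three-group chi-square at nominal 0.025. If it is significant, test combination vs P6 and patch vs P6 (title) and combination vs patch (section 3.3), each at 0.025. A smaller set of contrasts would do if it is named. Report every risk difference with a 97.5% CI, and say that:
- the intervals are individual (joint coverage about 92% to 93%), and descriptive if the gate stays closed;
- if joint coverage is wanted, a multiplier of 2.64 in place of 2.24 gives about 97.4%;
- a non-significant patch vs P6 result is not evidence of equivalence;
- if the analysis has already been run, the added contrasts are post hoc.

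**Cost.** A few SAP sentences and one table; no extra patients. At 70/70/90, power for the combination against one single arm is 90% at 0.05, 84% at the SAP's own 0.025, and 80% once gated; for both single arms it is 74%. In about 7% of trials a pair reaches 0.025 while the gate stays closed. Simultaneous intervals would widen the half-width at 70% vs 90% from 2.241 × √(0.30/80) = 13.7 points to 2.638 × √(0.30/80) = 16.2 points.

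### The SAP doubles both primary p-values; Holm's step-down gives the same 5% family-wise protection and never rejects less (a low-severity free improvement, not an error)

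*SAP*

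**What the plan says.** The SAP (Methods) applies a Bonferroni correction to two main outcomes, whether the patient vomited and whether she had nausea. It gives the rule in these words: "an adjusted p-value from each test equaled the nominal p-value multiplied by 2". Its Comments section calls these the primary outcomes: "The methods also clarify the adjustment for multiple testing on the two primary outcomes". Neither document ranks the two or describes a step-down, hierarchical or gatekeeping procedure.

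The test is also in SAP Methods: "chi-square was used for occurrence (yes/no) of nausea and vomiting overall all time points". I take this as one overall comparison of the three arms (2 degrees of freedom), since no pairwise tests are described.

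The SAP gives no significance level. The 5% comes from Protocol Section 3.3, which plans for "power of 90%, two-tailed test at 5% significance level to detect 90% success rate in the combination arm" against 70% in either single-therapy arm. That section does not say whether success means no nausea, no vomiting, or neither. On numbers it says: "There will be three groups each having 80 subjects enrolled for the study". Protocol Section 6 (Data Handling) allows up to 400 consents, and explains: "This number is to ensure that 80 subjects complete each study group below".

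**The concern.** With both p-values doubled, each outcome is in effect tested at 0.025 whatever the other shows. Once one outcome has been rejected at 0.025, the other can be tested at 0.05 without exceeding a 5% family-wise error. The SAP does not use that allowance.

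For example, take nominal p-values of 0.01 and 0.04. Bonferroni gives 0.02 and 0.08, so only one outcome is significant. Holm gives 0.02 and max(0.02, 0.04) = 0.04, so both are. At stake is a real effect on one of two co-equal primary outcomes being reported as non-significant when an equally protective rule would have accepted it.

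**Working it through.** **1. The plan's own figure.** Protocol Section 3.3: 90% v 70%, two-sided 0.05, power 90%. Let v = 0.9×0.1 + 0.7×0.3 = 0.30.
- Unpooled: n = (1.960 + 1.282)² × 0.30 / 0.2² = 78.8, so 79 per arm.
- Pooled: n = [1.960√(2×0.8×0.2) + 1.282√0.30]² / 0.2² = 82.0, so 82 per arm.

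The stated 80 is reproduced. It spends the full 5% on one success endpoint.

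**2. The same comparison at 0.025** (critical value 2.241, n = 80).
- Unpooled power, Φ(0.2/√(0.30/80) − z): 90.4% at 0.05 and 84.7% at 0.025.
- Pooled power, Φ([0.2 − z√(0.32/80)]/√(0.30/80)): 89.3% at 0.05 and 82.9% at 0.025.
- Restoring 90% at 0.025 would need 94 (unpooled) to 98 (pooled) per arm.

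The difference of 5.7 to 6.4 points shows what the level is worth in a pairwise comparison. Holm makes 0.05 available only to the outcome with the larger p-value, and only after the other is rejected.

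**3. Error control.** Holm rejects the smaller p-value if it is at most 0.025, and then the larger if it is at most 0.05.
- Both nulls true: a false rejection needs at least one p ≤ 0.025, with probability at most 0.025 + 0.025 = 0.05.
- One null true: a false rejection needs that outcome's p ≤ 0.05, with probability at most 0.05.

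Neither step uses the correlation. Everything Bonferroni rejects, Holm rejects too.

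**4. Where the gain comes from.** An outcome gains exactly when its own p lies between 0.025 and 0.05 and the other's is at most 0.025. The gain for rejecting both is therefore the sum of the two per-outcome gains, and the chance of at least one rejection does not change.

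**5. Simulation.** Three-arm chi-square, 80 per arm, two correlated binary outcomes generated from a bivariate normal with latent correlation 0.5 to 0.8. Only the 70/70/90% success rates (30/30/10% events) and the 80 per arm come from the protocol. Applying those rates to a named outcome is an assumption, and so are all the other rates and the correlations.

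| Event rates, outcome A | Event rates, outcome B | Power for B: Bonferroni → Holm | Power for both: Bonferroni → Holm |
|---|---|---|---|
| 30/30/10% | 30/30/10% | 87% → 91% | 77–79% → 85–86% |
| 30/30/10% | 20/20/5% | 77% → 84–85% | 69–71% → 80–81% |
| 30/30/10% | 15/15/4% | 54% → 65% | 49–51% → 62–64% |
| 30/30/20% | 30/30/20% | 20% → 23% | 7–9% → 11–15% |

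With 30/30/20% for A and 20/20/12% for B, power for B goes from about 17% to 19–20%.

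Check of step 4 in the first row at correlation 0.5: the per-outcome gains are 4.3 + 4.3 = 8.6 points, and power for both rises from 76.8% to 85.4%, also 8.6. The chance of at least one rejection is 96.8% under either rule.

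**6. Simulated error rates.** With no effect on either outcome (30% events in all arms), family-wise error is 4.6–4.9% under both rules. With 30/30/10% on one outcome and no effect on the other (15% in all arms), false rejection of the null outcome is about 2.4% under Bonferroni and about 4.5% under Holm.

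**The case against.** The strongest reply is that nothing is broken. The SAP names its two outcomes and states a valid correction whose only fault is to be conservative. No claim made under it would be unsound, and preferring a simple rule is defensible. That stands, and it sets the severity: this is lost efficiency.

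A second reply is that the size depends on inputs the documents do not give. That also stands. A reader might take 30/30/10% as the planned nausea rates and vomiting as the rarer outcome, the one bound to suffer. Protocol Section 3.3 does not define success, and neither document gives a rate for either outcome or a correlation. The "second" outcome can only mean the one with the larger p-value. If both effects are weak, the gain is 2–3 points per outcome.

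A third reply concerns timing. SAP Methods is written in the past tense. That does not show that results were known, but it does not rule it out. Moving to a less strict rule after seeing p-values would be a post hoc relaxation. This limits the recommendation without removing it.

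Finally, Holm raises the false-rejection rate for an outcome with no effect when the other is truly affected. This is the price of the added power, and it stays within the 5% limit.

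**Conclusion.** The point holds as a low-severity free improvement. For two unranked primary outcomes, Holm gives the same family-wise guarantee as the SAP's rule without further assumptions and never rejects less. With the protocol's success rates assumed for both outcomes, it is worth about 4 points per outcome and 8 to 9 points for establishing both. Across the other rates tried, the gain per outcome is about 2–3 to about 11 points. These figures rest on 80 per arm, an overall three-arm chi-square, a 5% level taken from the protocol, and assumed rates and correlations.

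Two stronger readings should be resisted. One is that Holm restores the planned 90% power. It cannot, because the first rejection still needs p ≤ 0.025. The 90% also refers to the combination against a single arm, a pairwise comparison that the SAP does not describe and that Holm across outcomes leaves untouched. The other is that the SAP's adjustment is wrong or makes its conclusions unsafe; it is valid and errs only towards caution.

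**What to change.** If results have not been seen, replace the adjustment sentence in SAP Methods with: order the two p-values; adjusted p(1) = 2 × p(1); adjusted p(2) = max(adjusted p(1), p(2)); compare each with 0.05. State the 0.05 in the SAP, which now gives no level.

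If results are already known, keep the Bonferroni values as primary and report the Holm values beside them, labelled post hoc.

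The cost is one sentence, with no extra patients or data. The one technical loss is that simple Bonferroni simultaneous confidence intervals would no longer match the tests exactly; the SAP specifies no such intervals. The pairwise comparisons behind the sample size need separate treatment.
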